- Being considered unsafe to participate as determined by the study physician;
- History of cardiovascular disease, diabetes, uncontrolled hypertension, untreated thyroid, renal, hepatic diseases, dyslipidemia or any other medical condition affecting weight or lipid metabolism;
- History of human immunodeficiency virus or hepatitis B or C (self-report);
- Taking medications affecting weight or energy intake/energy expenditure in the last 6
 months, including weight loss medications, antipsychotic drugs or other medications as
 determined by the study physician;
- Having abnormal blood chemistry (eGFR<45mL/min, AST or ALT >3 times the upper limit of normal) or as deemed significant by the study physician;
- Being a smoker or having been a smoker in the 3 months prior to their screening visit;
- Working night shifts;
- For participants completing the PSG studies, extreme early or extreme late chronotype as determined by the Munich Chronotype questionnaire³⁷. Participants completing the primary weight loss intervention will not be excluded based on chronotype;
- Night eating syndrome (at least 25% of food intake is consumed after the evening meal and/or at least two episodes of nocturnal eating per week) as assessed with meal pattern assessment questionnaire;
- For participants completing the PSG studies, greater than moderate sleep apnea (score high risk ≥ 2 or more categories on the Berlin Questionnaire). Participants completing the primary weight loss intervention will not be excluded based on Berlin OSA risk scores.
- For participants completing the PSG studies, use of medications affecting sleep (benzodiazepines and other sleep aids, as determined by study physician). Participants

- completing the primary weight loss intervention will not be excluded based on use of medications affecting sleep.
- Binge eating behaviors as identified by a score of >17 on the Binge Eating Scale (BES)³⁸.
- For participants in the optional Reproductive Hormone Sub-study: Current use of hormonal contraceptives, or use of hormonal contraceptives during the 4 months prior to the start of the weight loss intervention, previous diagnosis of polycystic ovarian syndrome.

C. Study Design and Research Methods

Informed consent, medical screening, labs, questionnaires, and baseline metabolic rate assessment.

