6-month follow-up assessments. Participants will continue to attend monthly group meetings during months 4-9. At 6-months following the completion of the weight loss intervention all subjects will be asked to come into the CTRC for repeat measures of RMR, body weight (scale) and composition (DXA). In addition, they will be asked to repeat questionnaires assessing adherence to the dietary intervention, satisfaction with the intervention, QOL (RAND-36), mood state (POMS-2), eating behaviors (TFEQ), and sleep (Berlin Questionnaire, Epworth Sleepiness Scale, Pittsburgh Sleep Quality Index, and Morningness -Eveningness Questionnaire, and Munich Chronotype Questionnaire). Due to the switch we made to ZOOM classes mid-intervention, we will send out a survey to the participants that asks about their experience with the online platform and how it compared to their in-person classes. We have also amended the focus group questions to ask about this as well.

Optional Reproductive Hormone Sub-study Procedures: Urine Collection to Evaluate Reproductive Hormones._These measures serve as markers of hypothalamic-pituitary-ovarian (HPO) axis function, which is evidenced to be suppressed in both women with obesity, as well as women with low energy availability (i.e., restricting energy intake or exercising intensely), which is the cornerstone of behavioral obesity treatment. Funding for these measures is provided by an NIH K award (HL 143039; PI [name]). Data from these participants will be combined with that being collected in another weight loss trial at the University of Colorado, Anschutz Medical Campus (COMIRB, 17-0369, PI, [name]) for statistical analysis, and thus are not included as outcome measures in the current protocol. Furthermore, the enrollment numbers for the main study do not need to be increased, as the target sample size for the sub-study research will not be reached from this study alone, and we will only target recruiting as many possible within the target enrollment for the main study.

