Description: A subset of 5-10 eumenorrheic (regularly cycling), pre-menopausal women not using hormonal birth control will undergo these optional additional procedures. Daily urine samples will collected over a complete menstrual cycle at baseline, and over 3 menstrual cycles at the beginning of the study (around months 1-3 of the intervention). Participants will be provided menstrual calendars to document overall menstrual cycle length during the weight loss intervention. During the urine collection period, they will be asked to collect daily, first void urine samples over the full menstrual cycle. Urine collection procedures will be based on those utilized by [name] (co-mentor) in a large (n = 847) cohort study³⁸, and those currently being used in 17-0369. Specimen collection kits, including a supply of pre-labeled polypropylene tubes (pre-filled with glycerol to a final concentration of 7%), an indelible marker pen, disposable plastic cups, and storage boxes will be provided to participants. Women will be instructed to collect their first morning voided urine into a cup, fill two tubes to the indicated line (5 ml), and place each tub into a box in the freezer within 2 hours of collection. A specimen log will be provided to allow participants to record any irregularities in the collection, such as a failure to remember to freeze the tube within 2 hours. Women will be instructed to collect specimens from the 1st day of menstrual bleeding to the 1st day of bleeding. Weekly telephone calls, SMS texts, or emails will be performed to encourage adherence to the protocol and answer any questions that may arise. Urine samples will be assayed in [name] laboratory for progesterone and estrogen metabolites (pregnanediol 3-glucuronide [Pdq], and estrone conjugates [E1c]), and mid-cycle LH and FSH using a flurometric immunoassay (AutoDELFIA: Perkin Elmer & Centaur XP: Siemans). Urinary concentrations of Pdg and E1c are closely correlated with serum concentrations of estradiol and progesterone allowing for frequent,

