minimally intrusive data collection. In addition, a tube of blood will be collected during the screening blood draw among these participants, and will be stored and assayed for Total Testosterone and Anti-Mullerian Hormone (AMH). This will allow us to examine predictors of obesity-related HPO axis suppression, and the effects of the behavioral weight loss intervention on HPO axis function distinct from the dysregulation of reproductive hormones associated with polycystic ovarian syndrome (PCOS). If, for whatever reason an additional tube of blood was not collected at a participants' screening visit, they will be asked to provide an additional blood draw in order to measure these assays. We will control for these hormone levels statistically, or potentially exclude data from participants whose labs are consistent with PCOS (AMH \leq 6, serum Total Testosterone <100 ng/dL), whichever approach is deemed most appropriate.

Justification for Inclusion. Gonadotropins and ovarian hormones are considered key regulators of energy homeostasis and body composition among women, and are suppressed in response to energy restriction, which reflects an adaptive response to strategically shift energy away from reproduction and toward survival during resource scarcity. Given the limited success of current behavioral approaches to treat obesity in women, it is important to evaluate whether compensatory mechanisms have evolved to protect reproduction during times of reduced energy intake that make weight loss more difficult and explain some of the variability in weight loss response. Thus, we will evaluate whether changes in reproductive hormones impact weight loss response, as well as explore whether diet patterns or weight reduction may induce changes in levels of reproductive hormones in a subset of eumenorrheic, pre-menopausal women not using hormonal birth control.

Recruitment. Male and female enrollment will rely on recruitment strategies that have proven successful in attracting volunteers to other projects the mentor and applicant have conducted, including projects involving controlled feeding. The recruitment strategies will include:

- -Fliers sent to households meeting specified demographics in geographic regions proximal to the University of Colorado (CU) Anschutz Medical Campus (AMC);
- -E-mail bulletins system-wide (e.g., CU AMC and University of Colorado Hospital [UCH]) e-mail blasts

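### The sub-study's optional PCOS exclusion is printed with upper limits only, so if used as written it always flags the lowest AMH and testosterone values and never flags values above both limits

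*Combined protocol and SAP*

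**What the plan says.** All references are to the Combined protocol and SAP.

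- **Purpose of the blood assays (Section IV.C, Optional Reproductive Hormone Sub-study).** Total testosterone and AMH are measured so that the team can "examine predictors of obesity-related HPO axis suppression" and can study the programme's effect on "HPO axis function distinct from the dysregulation of reproductive hormones associated with polycystic ovarian syndrome (PCOS").
- **Handling of the values (same section).** Two options are given. The first is adjustment: "We will control for these hormone levels statistically". The second is to "potentially exclude data from participants whose labs are consistent with PCOS". A bracket directly after these words gives AMH ≤ 6 and then "serum Total Testosterone <100 ng/dL), whichever approach is deemed most appropriate".
- **Who is in the sub-study.** Section IV.C describes "A subset of 5-10 eumenorrheic (regularly cycling), pre-menopausal women not using hormonal birth control". Section IV.B requires regular cycles for sub-study participants and excludes those with a "previous diagnosis of polycystic ovarian syndrome". It gives no laboratory limits.
- **Role of the data.** Section IV.C says the data will be pooled with those of another weight loss trial and "thus are not included as outcome measures in the current protocol". The Data Analysis Plan (Section IV.F) does not mention them.

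**The concern.** The bracket follows the reference to PCOS, so on an ordinary reading it defines which women may be excluded. Both conditions in it are upper limits. A rule of that shape covers everything from zero up to the limit, and neither condition can be met by a value above its limit.

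The women have already been screened for regular cycles and for no known PCOS. A further laboratory exclusion makes sense only as a way to find undiagnosed cases. If raised values are what point to PCOS, the printed rule runs against that purpose: it can set aside women with nothing to suggest PCOS and retain those it was meant to find.

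Three further details are missing. The AMH limit has no unit. Nothing says whether one limit or both must be met. No criterion or time point is given for choosing between exclusion and adjustment.

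At stake is which women's data this study passes to the pooled analysis. With 5-10 women, each one excluded is 1/10 = 10% to 1/5 = 20% of that contribution.

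**Working it through.** The plan gives no sample size, power or error rate for this rule, so there is no figure of its own to reproduce. The check is to apply the rule as printed.

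**Inputs (Section IV.C):** condition A is AMH ≤ 6 (no unit given); condition T is total testosterone < 100 ng/dL. The way they are joined is not stated, so both joins are tried.

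| AMH | Testosterone | A and T | A or T |
|---|---|---|---|
| ≤ 6 | < 100 | flagged | flagged |
| ≤ 6 | ≥ 100 | kept | flagged |
| > 6 | < 100 | kept | flagged |
| > 6 | ≥ 100 | kept | kept |

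The first and last rows do not depend on the join. Women at or below the AMH limit and below the testosterone limit are always flagged. Women above the AMH limit and at or above the testosterone limit never are. The two middle rows do depend on the join.

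**Grid check.** Illustrative values were AMH 0.5, 2, 4, 6, 6.1, 8, 12 and testosterone 10, 30, 60, 99, 100, 120, 160 ng/dL, giving 7 × 7 = 49 pairs. Four values of each satisfy the printed condition and three do not.

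- AND: 4 × 4 = 16 pairs flagged, 49 − 16 = 33 kept.
- OR: 3 × 3 = 9 pairs kept, 49 − 9 = 40 flagged.
- Under both joins the lowest pair (0.5 and 10) is flagged and the highest pair (12 and 160) is kept.

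These counts show how the rule behaves. They are not estimates of the share of women affected, because the grid is not a distribution of real values.

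**Could one misread sign explain it?** The AMH sign is a converted symbol in the text available for review; the testosterone sign is plain text. Suppose only the AMH sign were wrong, so that A became AMH ≥ 6. The testosterone condition would still be a ceiling. Under AND, a woman with AMH above 6 and testosterone of 100 or more would still not be flagged. Under OR, a woman at the lowest values of both would still be flagged through testosterone. A single correction therefore does not give a rule that works in one direction.

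**The case against.** The strongest reply is that this may never operate. Adjustment is named first and exclusion only as a possibility; if adjustment is used, the limits play no part. The data are also pooled with another trial, whose protocol is not available here and may hold the operative rule. No aim or outcome of this protocol depends on them. All of this stands, and it limits the point to a wording correction.

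A second reply is that the bracket may have been meant to give the values for keeping a woman, or that a sign was misread in conversion. Either is possible. Neither can be confirmed from the text: the bracket is attached to the women to be excluded, no other section restates the limits, and a misread AMH sign would leave the testosterone limit unexplained.

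A third reply is that the documents never say which direction of AMH or testosterone marks PCOS. That is correct. How the rule sorts women follows from the printed text alone; the judgement that it sorts them the wrong way rests on an outside assumption, declared as such.

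There are also stronger readings that a reader might infer and that the documents do not support:

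- *That the rule removes the women the sub-study was set up to study.* The markers of HPO-axis function are the urinary hormones (progesterone and estrogen metabolites, and mid-cycle LH and FSH). Nothing says that low AMH or testosterone marks suppression of that axis.
- *That every raised value is kept and every low value dropped.* A woman high on one assay and low on the other is kept under AND and flagged under OR.
- *That most of the women would be lost.* The documents give no distribution or reference range for either assay.
- *That the choice will be made with results in hand.* No timing is stated, and the blood is normally drawn at screening. The gap is that nothing fixes the choice beforehand.

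**Conclusion.** The point holds as a conditional one. If the exclusion option is used as printed, women low on both assays are always flagged and women above both limits never are, under either join. That does not fit the aim of separating out PCOS among women already screened for regular cycles and no previous diagnosis.

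The conclusion rests on three things: that the bracket defines the women to be excluded, that the signs are as they appear in the text, and that raised values point to PCOS. The last is an assumption from general knowledge.

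The size is small. It concerns an optional sub-study of 5-10 women, the share affected cannot be derived, and the feasibility, adherence and weight results of the main trial are untouched. It is worth correcting because a reversed filter would change what this study contributes to the pooled analysis.

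**What to change.** - Check the source document for a misread sign, the AMH symbol in particular.
- Have the sub-study investigators reconcile the direction of both inequalities with the stated purpose before any woman's data are excluded.
- State the AMH unit, and whether one limit or both must be met.
- Record whether exclusion or adjustment will be used before the outcome data are examined, in agreement with the plan for the pooled analysis.

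No replacement limits are proposed, and the choice between exclusion and adjustment is left to the investigators, who know the pooled sample size. The cost is about one line of protocol text, with no new data.

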- **Feasibility and tolerability of the interventions** assessed by enrollment and retention numbers, protocol related adverse events (AE's), and questionnaires assessing satisfaction, quality of life and mood.
- Adherence to interventions assessed both with self-report and with the use of a smartphone application in conjunction with continuous glucose monitoring.

Secondary Outcomes:

- Weight (scale) and body composition (DXA) obtained at baseline (prior to the weight loss intervention), at 12 weeks (following the weight loss intervention), and at a 6mo follow-up time point.
- Physical activity assessed by accelerometry
- Free-living sleep patterns assessed by wrist actigraphy
- Objective (in-laboratory) sleep recording using Compumedics Inc Siesta digital sleep recorders
- Meal timing and energy intake assessed by photographic food records
- Patterns in 24h glucose assessed by continuous glucose monitors over 7 days before and after the weight loss intervention
- Questionnaire based measures of appetite
- HqbA1c and lipids
- Resting metabolic rate and nocturnal energy metabolism by indirect calorimetery

B. Description of Population to be Enrolled:

Inclusion criteria.

- Adult males and females with a BMI of 27-45 kg/m² and weight stable over the previous 6 months;
- Age, 18-50 years old;
- Passing medical and physical screening, and analysis of blood and urine screening samples:
- Typical eating duration >12 hours per day (assessed by questionnaires);
- Own a smartphone
- Reside or work within approximately 30 minutes driving distance of CU-AMC (potential
 participants living outside of this driving distance could be included in the study at the PIs
 discretion).
- For participants in the optional Reproductive Hormone Sub-study: females, age 18-40, with regular menstrual cycles (between 18-40 days).

Exclusion criteria.

- Pregnancy or lactation for women (women who are >6 months postpartum with no plans of becoming pregnant in the next year and who are not currently lactating can be included; oral contraceptives will be allowed if medication has been consistent for the prior 6 months)
- Postmenopausal women (menopausal status will be assessed during the history and physical, with requirement of self-reported regular menstrual cycles for the last year; women who have undergone hysterectomy but with ovaries in place who continue to have regular menstrual symptoms can be included)

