Intervention Acceptability: Satisfaction with both the standard RCD and RCD+TRF program intervention will be assessed at week 12 and month 9 with a questionnaire that asks participants to rate on a 1-10 Likert scale how satisfied they were with specific domains of the intervention. The major domains that will be assessed are satisfaction with: 1) ability to adhere to caloric restriction and time restriction (for RCD+TRF group), 2) content of the dietary support curriculum, 3) content of the exercise support curriculum, 4) group meeting frequency and structure, and 5) weight loss achieved to date. Participants will also be asked in open-ended fashion to provide feedback on each domain of the intervention. We will also assess intervention acceptability by comparing the frequency of protocol related AE's, requirement for protocol modification, and attrition between groups.

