Consent. The consent process is part of the first orientation session, which takes about 1hr. Volunteers are either sent a copy of the consent form in advance or, if necessary, are given one at the start of the orientation; time is allowed to fully review of the consent form. Volunteers then meet with a member of the research team to a) have the study and what is expected of them explained in detail; b) discuss their reasons and motivation for wanting to participate to determine whether they are realistic; c) discuss any practical problems (e.g., scheduling conflicts, vacations) that could interfere with participation; d) have their questions answered; and e) demonstrate their ability to provide informed consent by describing their understanding of the major study goals and what is expected of them if they choose to participate. To avoid coercion, the presentation will stress that, 1) all research participation is voluntary, 2) subjects may withdraw at any time, and 3) the decision to participate or not participate will not affect the subjects' medical care or any benefits to which the subject is entitled.

Compensation. Subjects will be compensated up to \$400 for participation in the study. The compensation will be prorated as follows: Subjects will receive \$100 for completing the behavioral weight loss program and performing assessments at the 12 week time point and \$100 at the 6 month follow up visit. Subjects who choose to participate in the optional overnight PSG and nocturnal metabolism study will be compensated \$100 per study day, or a total of \$200. Subjects who choose to participate in the optional reproductive hormone sub-study will be compensated up to \$305 for participation in the study. Subjects will receive \$70/month of complete (>80%) daily urine collection, plus \$25 for tracking and reporting menstrual cycle length with menstrual calendars. In addition, participants who agree to participate in the focus groups at the end of the intervention will be compensated for their time in the form of \$50 Amazon gift cards.

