time restricted studies (SD of the sum = $\sqrt{3.7^2 + 3.4^2} = 5.0 \text{ kg}$). In our calculation, we assumed for the time restricted treatment group (RCD+TRF) a SD in-between the above lower and upper bounds of SD at 4.2kg. With these SD's, we have 80% power to detect a difference in mean weight loss between the two treatment groups of 3.5kg. This is slightly larger than the Gill and Panda study, but well within the range of the confidence interval of their result. In addition, this calculation is quite conservative. We will have power of 80% to detect an even smaller difference in weight loss between the groups, because in the final analysis we will adjust for baseline weight, which reduces the SD's in each of the groups and allows us to have power to detect smaller differences. The intervention will be modified if we are unable to recruit 30 participants, retain >70% of participants, or perform outcome measures within a 2-week window of the indicated time points in >90% of participants.

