Statistical Analysis: Efficacy Testing: Baseline demographic characteristics will be summarized by treatment groups using descriptive statistics. Any imbalance between groups will be examined using two-sample t-tests and Fisher's exact tests as appropriate. The primary analysis will use the ITT principle to test our study hypotheses under practical and realistic conditions when not all participants follow or complete the program. All randomized participants will be analyzed. A linear mixed effect model (LMM) will serve as the primary method to handle missing values. The normality assumptions will be evaluated and transformations used (e.g. square root and log) as appropriate. Change in weight is the primary outcome variable and others will be secondary outcomes. Consequently, no adjustment for multiple outcomes will be applied. P-values <0.05 will be considered significant. No interim analysis is planned. Any imbalance in baseline characteristics between groups that could potentially be a confounding factor for the outcome will be adjusted for in the statistical model (i.e., age, sex, level of PA achieved during intervention). Differences between groups in weight, fat mass, lean mass, MVPA, EI, sleep outcomes, and glucose variability will be compared using a LMM. Specifically, the test of time by group interaction will be used to assess efficacy. Pearson's correlations will be used to assess the relationship between sleep and nocturnal metabolism outcomes and longitudinal weight regain at 6 months. Variability of Major

Outcome Measures: Standard deviation and effect sizes will be determined based on the LMM model estimates to assist with planning the large-scale trial.

G. Summarize Knowledge to be Gained:

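### Read literally, the week-12 payment requires program completion, so people who stop classes lose the payment for the weight that the ITT analysis needs

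*Combined protocol and SAP*

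**What the plan says.** All references are to the combined protocol and SAP.

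- **Payment (IV.C, Compensation).** The first 100 dollars is "for completing the behavioral weight loss program and performing assessments at the 12 week time point". The next 100 dollars is paid "at the 6 month follow up visit. Subjects who choose to participate in the optional overnight PSG", and so on: the sentence ends at the visit and adds no program condition. The list is introduced by "The compensation will be prorated as follows", but none of its instalments pays for the week-12 assessments alone.
- **Analysis (IV.F, Statistical Analysis).** The efficacy analysis is by ITT, with everyone randomized included, so that the hypotheses are tested "under practical and realistic conditions when not all participants follow or complete the program". A linear mixed model is the primary way to handle missing values. No sensitivity analysis is named.
- **Weight schedule (IV.A, Secondary Outcomes).** "Weight (scale) and body composition (DXA) obtained at baseline", then at 12 weeks and at the 6-month follow-up.
- **Retention.** Retention numbers are part of the first primary outcome (IV.A). The intervention is to be modified if the study does not "retain >70% of participants, or perform outcome measures within a 2-week window" in more than 90% of participants (IV.F, Sample Size Justification). Acceptability is also judged by comparing "requirement for protocol modification, and attrition between groups" (IV.C, Intervention Acceptability).
- **People who leave.** IV.C (Post-intervention assessments) expects all participants to be measured after the 12 weeks. The only stated effort to reach people who dropped out concerns the focus groups.

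**The concern.** The clause joins two things that the rest of the plan keeps apart: staying in the program and being measured. This matters in two ways.

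First, the ITT analysis needs week-12 weights from people who stopped the program, and the literal wording withdraws payment for the week-12 visit from those same people. With so few scheduled weights, a missed week-12 visit leaves little for the model to work with.

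Second, retention is something this pilot is meant to measure and carry forward to the large trial. A payment for completing the program is an incentive inside that measurement. The retention rate would then partly reflect the payment and not only the acceptability of the intervention.

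**Working it through.** **1. The plan's own numbers.** Recruitment is 60 with 20% attrition: 60 × 0.80 = 48, or 24 per group, as IV.F states. Expected leavers are 60 − 48 = 12. The core payments are 100 + 100 = 200 dollars, and with 200 for the optional overnight studies they reach the stated 400. A leaver therefore forfeits half of the core payment under the literal clause.

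The plan's detectable difference of 3.5 kg at 80% power does not follow exactly from its SDs of 3.7 and 4.2 kg. With 24 per group the standard error is √((3.7² + 4.2²)/24) = √(31.33/24) = 1.14 kg. A two-sided t-test at 0.05 (sidedness is assumed) then detects 3.27 kg. An SD of 4.2 kg in both arms gives 3.47 kg. The stated figure is thus conservative, and the present point does not depend on it.

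**2. What a leaver contributes.** Someone who leaves and misses week 12 has a baseline weight only, until the 6-month follow-up. A baseline value alone adds almost nothing to the time-by-group test. Under missing at random, the model in effect treats that person's 12-week change as similar to that of others in the same arm. When the value is missing because the person left, there is little observed data with which to defend that assumption.

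**3. When the arm comparison is biased.** Let p be the proportion of an arm that leaves unweighed, and g the gap in mean weight loss between stayers and leavers, taken as equal in both arms. If leavers are treated like stayers, each arm's mean loss is overstated by p × g, and the difference between arms is off by (p in one arm − p in the other) × g. With equal p this is 0. The documents give neither p by arm nor g, so no size can be attached.

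**4. Information at stake.** With SDs of 3.7 and 4.2 kg, the detectable difference is:

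| Leavers weighed at week 12 | n per group | Detectable difference |
|---|---|---|
| none | 24 | 3.27 kg |
| half | 27 | 3.08 kg |
| all | 30 | 2.91 kg |

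This assumes that leavers share the same effect and SD. If they lose less weight, the gain is smaller.

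**5. Retention criterion.** 70% of 60 is 42, so more than 42 must be retained, and the plan expects 48. The payment is identical in both arms, so it bears directly on this absolute figure and has no evident direct effect on the comparison of attrition between arms.

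**6. Cost of paying leavers.** At 20% attrition: 12 × 100 = 1,200 dollars. At 30%: 0.30 × 60 = 18, and 18 × 100 = 1,800 dollars.

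**The case against.** The strongest reply is that the clause is loose wording for a milestone. IV.C runs the behavioral program over weeks 1 to 39, so completing it cannot literally be a condition for a week-12 payment; the phrase presumably means the initial 12 weeks. No attendance threshold is given, although the same paragraph sets one (more than 80%) for the urine collection. Nowhere does the text say outright that someone who stops classes goes unpaid. This stands as a reason for caution about intent. It does not make the wording safe: staff following it could withhold the payment, and no other instalment covers the visit.

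Three further replies also stand. The 6-month payment has no program condition, so leavers keep an incentive for a later weight that the model can use. Any payment for visits affects study retention, and acceptability is also judged by satisfaction ratings, adverse events, adherence ratings and focus groups. Finally, Specific Aim 1b says that the pilot is not powered for weight differences.

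A reader might infer that the clause biases the weight comparison by a calculable amount, for instance by taking the plan's 4.1 kg as the loss among stayers and assuming more leavers in one arm. The documents do not support this. IV.F gives 4.1 kg as an intent-to-treat mean, not a stayers' mean. The leavers' loss and the attrition by arm would both be invented. Such a figure would also compare weighing every leaver with weighing none, which is not the effect of a 100-dollar clause. The documents contain no data on how the payment changes behavior.

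**Conclusion.** The point holds as a cheap improvement to the design. As worded, the week-12 payment depends on program completion as well as assessment, which sits badly with an ITT analysis of everyone randomized and with retention as a primary outcome. Up to 12 of 60 week-12 weights are exposed at the plan's expected attrition. How many would be recovered by changing the clause is unknown.

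The direct effect is on absolute retention. Bias in the arm comparison is conditional: it needs leaving to differ by arm, in rate or in how leavers fare, and is zero otherwise. Its size cannot be derived from the documents. It would also go too far to infer that the comparison of attrition between arms is distorted, since both arms are paid alike.

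The conclusion rests on the literal reading of the clause and on the inference that payment influences attendance. It does not depend on whether weight change is a secondary outcome (IV.A) or the primary one (IV.F).

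**What to change.** For participants who have not yet reached week 12:

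- Reword IV.C (Compensation) and the consent form so that the 100 dollars is paid for performing the week-12 assessments, whether or not classes were attended or completed. This matches the 6-month payment.
- Tell anyone who stops classes that they are still invited to the week-12 assessments and will be paid for them.

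For all cohorts, report program completion and assessment completion as two separate figures by arm. This needs no new data collection beyond attendance and visit records.

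The change is about one sentence in each document. Extra payments are about 1,200 dollars at the expected 20% attrition and about 1,800 dollars at 30%, if every leaver attends. Both figures count all 60 participants, so they overstate the cost if some are already past week 12. Higher attrition than 30% would cost more. The downsides are a slightly weaker incentive to stay in classes and payment terms that may differ between earlier and later cohorts. The change does not address week-12 measurements lost under IV.C (COVID-19 Post Intervention Changes), which is a separate source of missing data.
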